4.3 Registration Requirements/Process

Not applicable.

4.4 Randomization and/or Dose Level Assignment

Each patient will be randomly assigned to either the remote perioperative telemonitoring or enhanced usual care arm. The assignments will be placed in sealed envelopes and opened sequentially. The PI, co-Is, participating clinicians and study CRN will be blinded to randomization assignment until envelopes are opened. The study CRN will share randomization assignment information with consented participants.

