4.0 Screening and Registration Procedures

4.1 Screening Procedures

All eligible patients who meet study inclusion criteria will be identified through the Division of Thoracic Surgery, Division of Surgical Oncology, Division of Urologic Oncology, and the Division of Gynecologic Oncology outpatient clinics. Clinical Research Nurses and CRAs will work with surgeons to identify eligible patients. Surgeons will notify the research staff, and staff will contact eligible patients to explain the study purpose, answer any questions, and ascertain interest in participation. If the patient agrees to participate, informed consent will be obtained in person or via mail, electronic mail, or other electronic applications (i.e. DocuSign) to obtain

electronic signatures from each patient per standard practice. Clinical Research Nurses and CRAs will be responsible for obtaining informed consent and study implementation.

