Figure 3: Study Schema

Study Procedures

Before Surgery:

The study schema is presented in Figure 3. Patients will be recruited from the surgical clinics at COH's Duarte campus only. Research staff will explain the study purpose, answer questions, and obtain informed consent. Patients will be enrolled at least 3-7 days before surgery. Following informed consent, the study CRA will assist patients with identifying a patient-owned engagement device (smartphone, tablet, computer), and assist with setup and initial testing of the Aetonix application on the device of choice. For patients who do not have an engagement device or have poor connections at home, a study Samsung tablet will be provided for the duration of the study. In our previous experience, only about 1.5% of patients had no device or inadequate internet access.⁴⁸ All patients will be provided with a Vivofit 4 and instructions. The study CRA will setup the device for patients and conduct initial testing to insure successful data transmission. Patients will wear the Vivofit 4 on their non-dominant wrist. Patients in both

arms will receive a package with the Aetonix physiologic PGHD home monitoring devices described previously. The study CRA will provide instructions (both verbal and in writing) on device use. All patients will be instructed to complete baseline assessment (T1) of PGHD and ePROs while at home.

Following completion of baseline assessment, participants will be randomly assigned to either the telemonitoring or enhanced usual care arm, using stratified and blocked randomization. Strata will be defined by diagnosis (upper GI, colorectal, hepatobiliary) and surgical technique (minimally-invasive versus open). Variable block sizes will be used to maintain approximate balance and pre-assignment masking. A pre-established randomization log will be created by the project biostatistician. The study staff will communicate group assignments to the patients.

For patients assigned to the telemonitoring arm, the alert/feedback system, monitored by the CRN, will be initiated for each patient. The system will be triggered on the occurrence of predetermined threshold events for physiologic PGHDs and ePROs, as described previously. Patients assigned to the enhanced usual care arm will use the Aetonix application to report

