13.2 Statistical Analysis Plan

13.2.1 Managing Data

PGHD, PROs and data on actionable patient care based on alert/feedback system and CRN monitoring (i.e. educated or counseled the patient, scheduled visits) will be initially stored in a secure, HIPPA-compliant cloud-based data storage system through Aetonix. We expect a total of 20 physiologic PGHD and ePRO evaluations per participant over the approximate 2 month study duration. With a total sample of 160, this yields more than 3,200 data collection encounters overall. We expect a large number of daily steps data observations per subject because functional recovery data will be continuously recorded on a daily basis over the study duration.

Data will be transferred on a daily basis from Aetonix to a REDCap (Research Electronic Data Capture) study database housed within COH and accessible only to the research team. The study biostatistician will work closely with Aetonix to coordinate real-time data transfer, auditing, and data cleaning. In the process of data transfer and mergers, the study biostatistician and Aetonix representatives will audit the data, clean the data, apply necessary formats in SAS statistical software, and export data into the REDCap database. A query system will be developed to address data validity and integrity by early identification of data collection inconsistency, data inaccuracy or incompleteness. This will be monitored by the biostatistician on a weekly basis throughout the project. Where feasible, validation rules (e.g. logic checks, format restrictions, min/max range, etc.) will be added to ensure that the data transferred and entered is valid and accurate.

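### Section 4.4's sealed envelopes make no provision for the six-stratum blocked scheme of section 5.1, and the safeguards that envelope concealment depends on are not stated

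*Combined protocol and SAP*

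**What the plan says.** **Section 4.4** describes the vehicle: "The assignments will be placed in sealed envelopes and opened sequentially". On masking it adds "The PI, co-Is, participating clinicians and study CRN will be blinded to randomization assignment until envelopes are opened", and on disclosure "The study CRN will share randomization assignment information with consented participants". It does not mention strata, blocks or section 5.1.

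**Section 5.1 (Study Procedures, Before Surgery)** describes the sequence. After the baseline assessment, "participants will be randomly assigned to either the telemonitoring or enhanced usual care arm, using stratified and blocked randomization". Then "Strata will be defined by diagnosis (upper GI, colorectal, hepatobiliary) and surgical technique (minimally-invasive versus open"; and "Variable block sizes will be used to maintain approximate balance and pre-assignment masking". The project biostatistician prepares the list in advance. Here it is study staff in general who tell patients their arm. The section does not mention envelopes.

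**Who does what.** Section 4.1 states that "Clinical Research Nurses and CRAs will be responsible for obtaining informed consent and study implementation". Section 5.1 has the research nurse monitor the alert system in the telemonitoring arm and has control patients told that nobody is monitoring their data. The protocol never calls the trial open-label, but in effect it is.

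**Registration.** Section 4.3 is marked not applicable, yet section 12.1.3.1 sends the reader there for the registration procedure.

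**Database.** Section 13.2.1 says "Data will be transferred on a daily basis from Aetonix to a REDCap (Research Electronic Data Capture) study database housed within COH". It describes storage and cleaning, not randomisation.

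**The concern.** Two things are at stake.

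*Stratification.* A stratified blocked list works only if each patient receives the next assignment from the list for his or her own stratum. Section 4.4 is the protocol's randomisation section, and it does not tell staff to do that. Someone following it alone could take the next envelope whatever the diagnosis or technique. Section 13.2.1.2 tests the primary endpoint with an unadjusted two-sample t-test. It allows optional covariates in the longitudinal model and gives age and sex as examples. Stratified allocation is therefore the only control for diagnosis and technique that the plan states.

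*Concealment.* Envelopes conceal allocation only as well as they are handled. The plan does not say that they are numbered, who holds or opens them, whether a log is kept, or whether a patient is tied to an envelope before it is opened. With section 4.3 empty, no registration step fills that gap. Recruitment is at one campus, so the same staff may see successive assignments, and they deal with the patients both before and after allocation.

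**Working it through.** **1. The plan's own figure.** Section 13.1.1 uses an effect size of 0.5, two-sided alpha of 0.05, 80% power and a two-sample t-test. The noncentral t calculation gives 63.77, so 64 per arm (power 0.801). With 20% attrition, 64 / (1 − 0.20) = 80 per arm, or 160 in total. This reproduces the plan and is not in dispute.

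**2. Strata.** 3 diagnosis groups × 2 techniques = 6. The plan does not print this number. With equal strata (assumed), 160 / 6 = 26.7 patients each.

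**3. The two sections compared.**

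| Item | Section 4.4 | Section 5.1 |
|---|---|---|
| Sequence | Not described | Stratified, variable blocks, biostatistician's list |
| Vehicle | Sealed envelopes, in sequence | Not described |
| One set per stratum | Not stated | Not stated |
| Who discloses the arm | Research nurse | Study staff |
| Numbering, custody, log, ID before opening | Not stated | Not stated |

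Nothing in one column contradicts the envelope method or the stratified list in the other. What is missing is the link between them.

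**4. Single stack, strata ignored.** When the overall allocation is balanced, the arm difference D in a stratum of n out of N patients has approximately

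Var(D) = n(N − n)/(N − 1) = 26.67 × 133.33 / 159 = 22.4, so SD = 4.73.

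Mean |D| ≈ SD × √(2/π) = 4.73 × 0.798 = 3.8 patients.

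Simulation with blocks of 4 and 6 gives 3.7.

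**5. Blocks within strata.** The difference cannot exceed half a block, which is 3 patients for blocks of 6. Simulation gives a mean of about 0.7.

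**6. Sensitivity.** The plan gives neither block sizes nor stratum shares. The simulations (3,000 to 5,000 trials of 160 patients per scenario) used blocks of 2 and 4 or of 4 and 6. Strata were equal or uneven (30, 20, 20, 10, 12 and 8%).

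| | Single stack | Blocks within strata |
|---|---|---|
| Mean arm difference per stratum | 3.6 to 3.8 | 0.6 to 0.75 |
| Average of the worst stratum | 7.5 to 7.6 | 1.3 to 1.6 |
| Chance that some stratum differs by 8 or more | 44 to 49% | 0% |
| Mean overall arm difference | 0.2 to 0.5 | 1.5 to 2.0 |

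**7. Effect on the planned t-test.** Assumptions: 128 evaluable patients, blocks of 4 and 6, and strata explaining 5, 10 or 20% of outcome variance; 6,000 runs each. Power at an effect size of 0.5 is 0.80 to 0.81 with a single stack and 0.81 to 0.82 with blocks within strata. Type I error is about 0.05 with a single stack and 0.03 to 0.05 with blocks within strata.

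**8. Guessing.** Someone who knows all past assignments in a sequence and always guesses the under-represented arm is right 68 to 72% of the time with blocks of 4, 6, 2/4 or 4/6. Chance alone gives 50%. This depends on the blocks, so it is the same for envelopes and for an electronic system.

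**The case against.** The strongest reply is that the sections complement each other. Section 5.1 supplies the list and 4.4 the container. Six sets filled from the biostatistician's list, each opened in order, satisfy both. That is correct. A reader might infer that the envelope method defeats the stratification, but the text does not support this: 4.4 never says there is a single stack. The imbalance figures therefore describe what would follow from one literal reading, not what the plan prescribes.

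The plan also states real safeguards. Envelopes are sealed, the investigators and the research nurse are masked until opening, block sizes vary, the biostatistician makes the list, and randomisation follows consent and a baseline that patients complete at home. A reader might also infer that nurses hold the envelopes and can foresee or reorder assignments. The documents do not say who holds or opens them, so this is an unclosed possibility and not a finding.

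Nor would a single stack invalidate the primary test. Step 7 shows type I error held and power almost unchanged. The loss would be comparability within diagnosis and technique.

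Finally, the REDCap database is described for data storage only, so a randomisation function cannot be presumed. Well-prepared envelopes can serve a single-campus pilot.

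What remains is that masking until opening is only as good as the handling before opening, and the plan does not describe that handling.

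**Conclusion.** The point holds as a gap between two sections, together with a concealment method that can be improved cheaply. Section 4.4 does not provide for the six-stratum scheme of 5.1 and omits the handling rules that envelope concealment needs.

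If envelopes were used as a single stack, the mean within-stratum arm difference would rise from about 0.7 to about 3.7 patients, with overall 1:1 balance kept. These figures assume equal strata and blocks of 4 and 6; the ranges in step 6 show that they change little under the alternatives tried. No figure can be put on the concealment risk from the documents. It is reduced by the stated safeguards but not removed, because the trial is in effect open-label and research nurses consent patients, disclose the arm and monitor the alerts.

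The documents do not show that stratification fails, that allocation has been or will be subverted, or that the primary test is invalid. The sample size stands.

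**What to change.** Rewrite the allocation sentence in 4.4 and refer it to 5.1:

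- **Preferred.** The biostatistician's stratified, variable-block list is held in a central electronic system. This can be the REDCap study database if its randomisation function is available, which the sponsor should confirm. Staff enter the patient ID and stratum and confirm that T1 is complete. The system then returns and time-stamps the assignment.
- **If that is unavailable, or as a downtime backup.** Use six sets of opaque, sequentially numbered envelopes, one per stratum. Someone already on the team who does not enrol patients holds them. The patient ID and date are written on the envelope before it is opened, and a log is kept.

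In the same edit, make 4.4 and 5.1 agree on who tells patients their arm, and either fill in section 4.3 or remove the reference to it in 12.1.3.1.

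The cost is a short text change, some set-up time (the documents give no basis for an estimate) and the need for system access at the moment of randomisation. The change prevents envelopes being opened early or out of order and leaves an audit trail. It does not prevent guessing from known assignments within a block, and it does not change the sample size.

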 - e. Blood pressure – systolic blood pressure <90 (<85 if last systolic blood pressure at discharge was <100) or >180 ; diastolic blood pressure ≥ 95 (low alert) and ≥ 100 (high alert).
 - f. Functional activity - daily steps of ≤ 1500 .
2. Patient-Reported Outcomes:
 - a. One or more symptoms rated 4 or greater (moderate-severe intensity)
 - b. One or more QOL questions rated moderate, severe, or unable to accomplish

Pathway for RN Triage and Management:

1. Patients will measure their vital signs once a day after discharge at 9 AM. Patients will have the option of measuring their vitals again at 3PM if they choose to
2. If RN identifies deviations from a priori thresholds, they will:

- i. Call the patient, and ask them to repeat all vital signs.
 - ii. Ask the patient if they are having: nausea, vomiting, fevers worsening pain, spreading redness around their incision, new or worsening drainage from their incision, chest pain, shortness of breath, difficulty breathing. Also ask if the patient is drinking at least 1.5 liters of fluid a day.
3. If vital signs on re-check are beyond threshold values but all the above patient-generated metrics are normal/negative, relay information to the on-call physician or health care provider for further determination of next course of action.
4. If vital signs on re-check are beyond threshold values and at least one of the patient-generated metrics is abnormal/positive, the patient should be evaluated within the next 24 hours. Relay information to the on-call physician or health care provider to determine exactly when/how evaluation should take place.
5. Evaluation within the next 24 hours may be:
 - i. Repeat vital signs in a pre-defined period of time to be reviewed by a health care provider
 - ii. Planned repeat phone conversation with the patient
 - iii. Clinic visit that day or the next business day
 - iv. Evaluation in the evaluation and treatment center or other urgent care/emergency department

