12.1.3 Data Collection Forms and Submission Schedule

All data will be collected from home monitoring devices, wearable devices (pedometer), and electronic PROs. Data will be sent to the location identified in Section 12.1.1 and stored in a secure location.

EQ-5D-5L - This validated tool evaluates five QOL variables: mobility, self-care, usual activities, pain/discomfort, and anxiety/depression. One final item evaluates overall health state using a visual analogue scale with the end points labeled best to worst imaginable health state (0-100 numeric value). The EQ-5D has been widely used in clinical trials and also used in quality-adjusted survival analysis.²⁴⁻²⁷

MD Anderson Symptom Inventory (MDASI) - This is a brief, validated measure of 13 common cancer-related symptoms with severity of each rated on a 10-point scale. Patients also rate how much their symptoms interfered with 6 common functional domains. The MDASI has several advantages over other symptom-assessment scales in that it applies broadly across cancer types and treatments, is easy for patients to complete, and includes items related to symptom interference with daily life. Cronbach alpha reliability ranges from 0.82 to 0.94.^{28,29}

Sociodemographic and health status – This tool covers social and demographic factors, including patient's age, sex, race/ethnicity, education, marital status, living situation, employment, income, religious preference, tobacco history, and symptoms. Patients will complete the tool at baseline.

Satisfaction Tool – This patient self-reported measure contains 13 questions designed to assess satisfaction with the electronic assessment. Data captured include: 1) ease of use of web-based surveys and wristband device; 2) Feedback on items in the web-based surveys that are distressing or difficult to comprehend; 3) Feedback on length of surveys and timing of administration; and 4) Suggestions for items that were not covered but should be added. It will be administered at the Day 30 post-discharge assessment. Both arms of the study will undergo this.

Surgical Outcomes: Comprehensive Complications Index (CCI) - The CCI® summarizes the entire patient postoperative experience with respect to complications (on a scale from 0 to 100), and is based on the established Clavien-Dindo classification. The CCI® was validated in a study with 1299 participants, and external validity was tested in a randomized trial evaluating pancreas, esophageal, and colon resections.^{31,32}

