13.0 Statistical Considerations

13.1 Study Design

13.1.1 Sample Size Calculation and Power Analysis

We will need 128 patients (64 per arm) to detect an effect size of 0.5 in the primary outcomes as described in Aim 2 (postoperative complications, lower readmission rates, improved symptoms, QOL, and functional recovery) between the two groups, with a two-sided 0.05 significance level using a two-sample t-test and at least 80% power. We will enroll a total of 160 (80 per arm to account for an expectation of 20% attrition. Thus, we will have sufficient power for all primary outcomes, including our primary endpoint of postoperative complications.

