In order to protect PHI data the patients will be labelled as Subject # e.g. Patient001, Patient002. Only the PI on the study and CRAs and CRN will have access to Patient Identifiers. The CRNs will have the ability to document any response to the alerts of abnormal patient generated health data as a research progress note in EPIC. The PI and the CRAs and CRNs will have access to the Aetonix app on their COH provided devices. There will be no data integration into EPIC. The devices used to transmit the patient generated health data (blood pressure, weight, temperature, pulse oximetry and heart rate) do not store any of the data and are not linked to any patient identifiers. The vivofit4 used to capture the patient steps will require that patients sign up on the Garmin website and agree to the company terms of use. These will not be linked to clinical data in any way.

13.2.1.1 *Handling Missing Sessions and Data*

Subjects with missing items among dependent variables will be compared with subjects having non-missing items to determine whether there is any bias underlying the missing data (i.e., whether data are

missing at random or can be accounted for by other variables). We will consider multiple imputation (MI) for estimating missing responses and covariates, which can be done using PROC MI in the SAS 9.4 system of software for analysis. The estimates obtained across (10 to 20) multiply imputed data sets can be combined using proc MIANALYZE, which provides valid standard errors for making inferences using the missing at random assumption.

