Feasibility will be assessed through: 1) the ratio of eligible participants to those enrolled and those who declines participation; 2) reasons for non-participation; 3) number of scheduled study encounters completed; 3) attrition rate between pre- and post-discharge; 4) reasons for attrition/dropout; 5) the ratio of all participants to those who completed $\geq 70\%$ of the study; These data will be descriptively reported and analyzed. Qualitative data on acceptability from exit interviews will be analyzed using the conventional content analysis approach.⁶⁵ This approach is used to describe a phenomenon where existing theory or research literature is limited. Data from the audio-recorded interviews will be transcribed and analyzed using HyperRESEARCH™ qualitative software. Transcripts will be imported allowing for the development of analytic categories, data coding, and review of coded data. All data will be read repeatedly to achieve immersion and obtain a sense of the whole. Then, data will be read word by word to derive codes. Codes will then be sorted into themes based on links and relationship. Separate investigators ([name] and [name]) will conduct a final validation review of the codes and themes to ensure consistency and clarity across all qualitative data. Data discordantly coded will be discussed for refinement and consensus purposes.

Specific Aim 2: Determine the preliminary efficacy of the remote perioperative telemonitoring intervention on surgical outcomes, healthcare utilization, PROs, and functional recovery.

Hypothesis 2.1: Patients randomized to the telemonitoring arm will experience reduced severity (grade) of postoperative complications, lower readmission rates, and improved symptoms, QOL, and daily steps.

For Specific Aim 2, the primary endpoint is the change in Comprehensive Complications index (CCI) from discharge to day 30 post-discharge. First, change in CCI will be computed. A two-sample t-test will be conducted to determine if there is significant difference between mean CCI of the intervention arm and the control arm. Trends in CCI scores will be explored over time (T2-T5). Exploratory within subjects' correlation will be examined using Pearson correlation between adjacent time points. A random-effects model will be used to study group differences in mean over time. Other variables (e.g., age and sex) may be included in the model to adjust for possible confounding.

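### Alert-driven nurse contact occurs in one arm only and CCI grading is not masked, so the primary comparison can mix a treatment effect with unequal detection of mild complications

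*Combined protocol and SAP*

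**What the plan says.** **Masking.** Section 4.4: "The PI, co-Is, participating clinicians and study CRN will be blinded to randomization assignment until envelopes are opened". Section 5.1 places assignment before surgery, after the baseline assessment, and patients are then told their arm.

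**Contact that differs by arm.** Under Section 5.1 the alert system is switched on for telemonitoring patients. When a threshold is crossed the nurse calls, has vital signs repeated, and follows a script: "Ask the patient if they are having: nausea, vomiting, fevers worsening pain, spreading redness around their incision", then wound drainage, chest pain and breathing. If the repeat values stay out of range and a symptom is present, the patient is to be evaluated within 24 hours. Section 13.2.1 lets the nurses "document any response to the alerts of abnormal patient generated health data as a research progress note in EPIC". Controls send the same data, but are told that nobody is watching it and that they should use the usual reporting routes.

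**Ascertainment that is shared.** The study calendar (Section 10.0) and Table 1 (Section 11.1) schedule MDASI, EQ-5D-5L and CCI at the same times in both arms. The chart audit in Section 12.1.3 is not limited by arm and reaches outside emergency care with the patient's permission.

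**Endpoint and test.** Section 12.1.3 says the CCI "summarizes the entire patient postoperative experience with respect to complications". Section 13.2.1.2 states that "the primary endpoint is the change in Comprehensive Complications index (CCI) from discharge to day 30 post-discharge", and then: "A two-sample t-test will be conducted to determine if there is significant difference between mean CCI of the intervention arm and the control arm". It has no sensitivity analysis for detection. No section names the grader. The CCI data source is also unclear: Section 12.1.3 opens by listing home devices, the pedometer and ePROs as the sources, while its chart audit lists readmissions, their reasons, ER visits and clinical and surgical characteristics. Section 11.1 mentions post-operative events only in passing.

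**The concern.** A complication enters the CCI only if someone learns of it and grades it. After discharge, which is the window of the primary endpoint, one arm has an extra route by which a mild wound problem or fever can be noticed and written down. The other arm relies on the patient to report it. Because the CCI is meant to cover the whole complication experience, mild events of this kind add to the score.

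Two distortions are possible, and they oppose each other. Extra detection raises recorded CCI in the telemonitoring arm and works against the intervention. Grading by someone who knows the arm could favour it. The plan has no provision that would reveal either.

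This matters in a pilot too. Section 1.0 says the findings will be used to identify the effect size for a Phase III sample size, so a distorted CCI difference would carry straight into that calculation.

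**Working it through.** **1. The plan's own figure.** Section 13.1.1: "We will need 128 patients (64 per arm) to detect an effect size of 0.5 in the primary outcomes", "with a two-sided 0.05 significance level using a two-sample t-test and at least 80% power". For a two-sample t-test the noncentrality is d × √(n/2). With d = 0.5 and n = 64 this is 0.5 × √32 = 2.83 on 126 degrees of freedom, giving power of 80.1%. Solving for 80% power gives 63.77, so 64 per arm. For attrition, 128 / 0.80 = 160. The stated figures reproduce, so the issue is bias and not sample-size arithmetic.

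**2. Routes by which a post-discharge complication can become known.**

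| Route | Telemonitoring | Enhanced usual care |
|---|---|---|
| Scheduled MDASI, EQ-5D-5L, CCI time points | Yes | Yes, same times |
| Home vital signs sent in | Yes, with alerts | Yes, no alerts |
| Nurse call with symptom script | After a threshold breach | None by design |
| Evaluation within 24 hours after an alert | Possible | None by design |
| Alert-response research note in EPIC | Possible | None |
| Chart audit | Yes | Yes |

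**3. Scale of the extra contact.** The preliminary study in Section 2.4 had alerts in 54 of 160 PRO encounters (33.75%). Assume that rate carries over to four post-discharge assessments (days 2, 7, 14 and 30):

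- 80 patients: 80 × 4 × 0.3375 = 108 PRO alerts.
- 64 patients: 64 × 4 × 0.3375 = about 86.

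By design there are none in controls. This is rough. The pilot figure is for the first week, its QOL trigger is worded differently from the present one, and vital-sign and step alerts are left out.

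**4. What a shift would do.** The documents give no CCI standard deviation and no detection rate, so the shift b is an assumption, in SD units of whichever CCI measure is tested. A shift of 0.10 arises, for example, if 10% of one arm gain 1 SD (0.10 × 1) or 20% gain 0.5 SD (0.20 × 0.5). With 64 per arm:

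- Power when the shift hides part of a true 0.5: noncentrality (0.5 − b) × √32. At b = 0.10 this is 0.4 × 5.657 = 2.26.
- Two-sided rejection rate with no true effect, shift in either direction: noncentrality b × √32. At b = 0.10 this is 0.57.

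| b (SD) | Power, true d = 0.5 | Rejection rate, no true effect |
|---|---|---|
| 0 | 80% | 5.0% |
| 0.05 | 71% | 5.9% |
| 0.10 | 61% | 8.7% |
| 0.15 | 50% | 13.4% |
| 0.20 | 39% | 20.2% |

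**5. Carry-over to Phase III.** If a true 0.5 were observed as 0.4 (b = 0.10), the same 80% power calculation would give 100 per arm instead of 64.

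**The case against.** **Nurse contact is the treatment, and open-label delivery cannot be avoided.** Both are true. The difference in contact is not an error, and nothing here asks for it to be removed. The gap is that outcome ascertainment is neither masked nor separated from it.

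**Much of the ascertainment is common to both arms.** This stands in part. Controls complete the same symptom instruments and have the same CCI time points and chart audit. Section 5.5 also has research staff reviewing participants' responses without restriction by arm and alerting the surgeon to serious conditions. It would be wrong to say that controls are never asked about symptoms. But none of these provisions gives them threshold calls or alert notes. Section 5.5 also sits badly with the message to controls in Section 5.1 that their data are not monitored, and the two must be reconciled.

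**A reader might infer that complications are graded by someone who knows the arm.** The documents do not say so, because no grader is named. Section 4.4 describes concealment before assignment and is not itself an error. What can be said is that every clinical role it lists is unmasked afterwards and no masked assessor is provided.

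**The remedies are imperfect.** This stands. Co-investigators are among those unmasked, so removing notes from an extract does not blind someone who already knows the allocation. Visits triggered by alerts produce clinical notes, which a same-source rule would still count. Severe complications are fewer, and preventing escalation is part of the intended benefit, so an analysis restricted to them answers a narrower question with less precision.

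**Conclusion.** The concern holds in limited form. The plan provides no masked CCI grading, one arm has an additional route to detecting mild post-discharge complications, and the primary t-test has no check for it. A difference or a null result in CCI is therefore harder to interpret than it needs to be.

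The direction and size of any bias cannot be derived from the documents. The 0.10 SD figures (power 80% to 61%; false-positive rate 5% to 8.7%) show sensitivity and are not estimates. A reader might infer that the trial is biased against the intervention, or that its power is known to be lower than stated. Neither follows, since the two mechanisms oppose each other and no detection rate is given.

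This should be fixed because it is cheap. It does not undermine the design or change the 128 evaluable and 160 enrolled.

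**What to change.** In Sections 12.1.3 and 13.2.1.2:

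- **(a) Sensitivity analysis.** Prespecify a repeat of the primary comparison restricted to post-discharge complications of Clavien-Dindo grade III or higher, which nurse calls are least likely to add. Report the arm difference with a confidence interval and acknowledge that it is less precise.
- **(b) One counting rule.** In both arms, count complications only from clinical notes and the common post-discharge assessments (T3 to T6 in the study calendar, days 2 to 30). Exclude events known only from alert-response research notes. Record how each event was first detected.
- **(c) Grading.** Name the grader. Where an existing team member neither handled alerts for the patient nor treated that patient, have that person grade from an extract with arm and alert notes removed. Describe this as reduced-knowledge grading and not as full blinding.

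Also reconcile Section 5.5 with Section 5.1 on whether control responses are reviewed.

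**Cost.** SAP wording, some research-associate time for the extracts and one more analysis on data already collected; no added staff and no change in sample size. The downsides are that a few mild events go uncounted, (b) is only a partial remedy because alert-triggered visits create clinical notes, and (a) rests on fewer events.
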